3.0 Inclusion/Exclusion Criteria

Inclusion Criteria

- Histologically proven cancer of the head and neck cancer
- Stage 3 or 4 under the AJCC and IUCC staging System OR patients with Stage 1 or 2 disease who will receive radiation equivalent to patients with Stage 3 or 4 disease
- Planned primary or adjuvant chemoradiation therapy
- Willing and able to provide informed consent
- Age \geq 21 years
- English speaking

Exclusion Criteria

- Currently on gabapentin
- Prior non-tolerance of gabapentin
- History of seizure disorder

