2.0 Specific Aims

Specific Aim 1: To determine whether Gabapentin used as a preventive measure during chemoradiation can reduce radiation-induced mucositis associated pain in head and neck cancer patients as measured by: 1) pain scores on the Vanderbilt Head and Neck Symptom Survey (VHNSS version 2.), and 2) analgesic use.

Hypothesis 1.1: Compared to controls, patients using Gabapentin during radiation-based therapy will have a 1.5 point decreases in self-reported oropharyngeal pain (on a scale of 0 to 10) week six of radiation.

Hypothesis 1.2: Compared to controls, patients using Gabapentin during radiation-based therapy will have a 20% decrease in opioid use (as measured in morphine equivalents) at week six of radiation.

Specific Aim 2: To determine whether pain control is associated with weight loss (in pounds) and duration of use of percutaneous endoscopic gastrostomy utilization (in days).

Hypothesis 2.1 Patients with less pain will have decrease weight loss.

Hypothesis 2.2 Patients with less pain will have a shorter duration of PEG placement.

Specific Aim 3: To assess the safety (grade 3 or 4 adverse events) and tolerability of using gabapentin (discontinuation of drug due to side effects - yes or no).

Specific Aim 4: To correlate pain severity with frequency and severity of general systemic symptoms.

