4.0 Enrollment/Randomization

A total of 150 patients planned for primary and adjuvant radiation with or without chemotherapy will be recruited. These patients will be identified in the Vanderbilt Oncology Clinic and at head and neck tumor board. Study staff will approach patients to discuss the study and the possibility of patient participation therein. The objectives and requirements of the study will be described to the patients and any questions will be answered. Interested patients will be given consent for to review. If the patient volunteers to participate in the study, the consent will be signed and they will be given a copy for their records. The original copy will be retained in the study files. The patient will be assigned to the usual care or usual care plus gabapentin arm of the study according to the next group assignment specified in the randomization list generated via the use of a computer-generated, permuted block program developed by Co-I [name].

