Appendix H: Disease and Treatment Data Form

Diagnosis

Date ____ / ____ / ____ (mm/dd/year)

Type

(Location/Originating cancerous lesions)

- (1) Nasal cavity
- (2) Paranasal sinuses
- (3) Oral cavity
- (4) Nasopharynx
- (5) Oropharynx
- (6) Hypopharynx
- (7) Larynx
- (8) Salivary gland
- (9) Other _____

Stage: T ____ N ____ M ____

- X
- 0
- I
- IIa
- IIb
- IIIa
- IIIb
- IVa
- IVb
- IVc

Surgery

Date ____ / ____ / ____

Type:

- (1) Standard RND (radical neck dissection)
- (2) Bilateral RND
- (3) Modified RND
- (4) Modified neck dissection
- (5) Functional neck dissection
- (6) Selective neck dissection
- (7) Other _____

Number of dissected lymph nodes ____

Number of positive lymph nodes ____

Radiation Therapy

None

Some

Site (1) _____ Dosage _____ cGy

Site (2) _____ Dosage _____ cGy

Site (3) _____ Dosage _____ cGy

Site (4) _____ Dosage _____ cGy

Begin date ____/____/____

End date ____/____/____

Pattern of therapy _____

Days on to days off ratios _____

Chemotherapy

Induction Yes No

None

some

Number of cycles _____

Begin date ____/____/____

End date ____/____/____

Type:

(1) Taxol

(2) Carboplatin

(3) Other: _____

ChemoXRT

None

Some

Begin date ____/____/____

End date ____/____/____

Type:

(1) Taxol

(2) Carboplatin

(3) Other: _____

Total treatment received

(1) Induction+ ChemoXRT

(2) ChemoXRT

(3) Surgery + ChemoXRT

(4) Surgery + Radiotherapy

(5) Surgery only

(6) Radiotherapy only

(7) other (please list) _____

Treatment-related complications _____

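### Tumour site and primary versus adjuvant setting are neither stratification factors nor model covariates, which forgoes precision on H1.1 and H1.2 but causes no bias

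*Combined protocol and SAP*

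**What the plan says.** **Who enters.** Section 3.0 requires "Histologically proven cancer of the head and neck cancer". Patients must have stage 3 or 4 disease, or be "patients with Stage 1 or 2 disease who will receive radiation equivalent to patients with Stage 3 or 4 disease". The treatment criterion is "Planned primary or adjuvant chemoradiation therapy". No criterion refers to primary site.

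**How they are allocated.** Section 4.0 assigns the next entry on a "randomization list generated via the use of a computer-generated, permuted block program". It names no stratification factor.

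**What is measured.** H1.1 in section 2.0 expects "1.5 point decreases in self-reported oropharyngeal pain (on a scale of 0 to 10) week six of radiation". H1.2 concerns opioid use at the same week. In the Appendix B questionnaire, items 22 to 24 ask about pain in the mouth or throat.

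**How it is analysed.** Section 10.0 specifies mixed-level general linear models. Baseline VHNSS pain is the only covariate named.

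**What is recorded.** The Appendix H form has a site list (one entry is "8) Salivary gland"), a surgery block and a total-treatment field that separates surgical from non-surgical courses. Both copies of the Appendix I calendar mark this form at baseline.

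**The concern.** A population that mixes primary sites, and mixes post-operative with non-operated patients, may vary in mouth and throat pain for reasons unrelated to gabapentin. If a factor known before randomisation explains part of that variation and the model omits it, the variation stays in the residual. The confidence interval is then wider than it need be. Without strata, the arms can also differ by chance in their mix of sites or settings, and a model containing only baseline pain does not remove the effect of that difference.

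Baseline pain may be a poor substitute. It is measured before radiation, whereas mucositis pain develops during it (section 1.2 puts onset two to three weeks into treatment). Neither calendar marks the VHNSS at baseline, so even this one covariate may lack a scheduled source.

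At stake is the width of the interval for H1.1 and H1.2, not the validity of the comparison.

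**Working it through.** **Inputs from section 10.0:** SD 2.8; difference 1.5 points; 60 analysed per arm; two-sided alpha 0.05; stated power 80%.

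**Assumed, because the plan gives no case mix:** a subgroup making up q = 20% of patients whose mean pain is D = 2 or 3 points lower, with the overall SD of 2.8 already including this spread.

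**Step 1: the plan's own figure.** SE = 2.8 × √(2/60) = 0.511. Then 1.5/0.511 − 1.960 = 0.974, so power is 83.5% (normal approximation; 82.9% by two-sample t-test). The stated 80% would need only 55 per arm (56 by t-test). The plan is slightly conservative here, which fits its remark about allowing for more variable data.

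**Step 2: share of variance due to the subgroup.** R² = q(1 − q)D²/2.8².
- D = 2: 0.20 × 0.80 × 4/7.84 = 0.082
- D = 3: 0.20 × 0.80 × 9/7.84 = 0.184

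**Step 3: after adjustment.** Residual SD = 2.8 × √(1 − R²); power is for 1.5 points at 60 per arm (normal approximation).

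| Model | Residual SD | SE | Power | Equivalent n per arm, 60/(1 − R²) |
|---|---|---|---|---|
| Unadjusted | 2.80 | 0.51 | 83.5% | 60 |
| Adjusted, D = 2 | 2.68 | 0.49 | 86.5% | 65 |
| Adjusted, D = 3 | 2.53 | 0.46 | 90.1% | 73 |

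**Step 4: size of chance imbalance.** The between-arm difference in the subgroup's share has SD √(2 × 0.20 × 0.80/60) = 0.073, about 7 percentage points. One SD of imbalance moves the estimate by 0.073 × 2 = 0.15 or 0.073 × 3 = 0.22 points. That is about 0.3 to 0.4 of the 0.51 standard error. It is one component of that standard error, not an error on top of it.

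**Limits of the illustration.** It takes 2.8 as the residual SD before any covariate. Baseline pain, if collected, will absorb some variance, and the extra gain from site will be smaller where the two overlap. Treatment setting is not included in the figures. No SD is given for opioid use, so the gain for H1.2 cannot be quantified.

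**The case against.** The strongest counter-argument is that nothing is wrong as it stands. Randomisation protects the comparison, the standard error reflects chance imbalance, and the sample size has a small margin. That all stands. It is also fair that the documents do not show how strongly site or setting predicts pain. If they predict nothing, the proposal gains nothing, although it costs only two degrees of freedom in an analysis of 120 patients.

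A reader might infer something stronger: that admitting every head and neck primary brings in patients with little mucositis to prevent, which dilutes the 1.5-point effect and calls for a criterion on the radiation field. The documents do not support this.
- They give no case mix, so the share of such patients is unknown.
- The Appendix H site list is a generic checklist. It also offers stage 0, no radiation and surgery only, so an entry on it does not show expected enrolment.
- The prior studies behind the mean of 4.5 and SD of 2.8 are not described, and 1.5 points may already be an average over an unselected population.
- Aim 1 asks about head and neck cancer patients generally, so broad entry matches the question.
- The stage rule and the chemoradiation criterion already select for more intensive treatment, although section 4.0 recruits for "A total of 150 patients planned for primary and adjuvant radiation with or without chemotherapy will be recruited", and the two sections need reconciling.

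A reader might also link missing strata to dilution or bias. Stratification changes neither who is enrolled nor the expected difference between arms.

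**Conclusion.** The point holds as a missed gain in precision. The plan has one unstratified list and one covariate, while two plausible predictors of the outcome can be known before randomisation and already have a place on the study's forms. Under the assumed 20% subgroup scoring 2 to 3 points lower, adjustment is worth about 3 to 7 percentage points of power, or the equivalent of 5 to 13 extra analysed patients per arm. The true gain could be larger, smaller or nil. There is no bias, the power statement in section 10.0 is not undermined, and eligibility does not need to change on this ground.

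**What to change.** 1. In section 10.0, prespecify two covariates for the H1.1 and H1.2 models in addition to baseline pain: primary site group, and primary versus adjuvant setting.
2. Define the site groups before outcomes are compared by arm, according to expected exposure of mouth or throat mucosa. A split of oral cavity and oropharynx against everything else fits less well, because items 22 to 24 also cover throat pain and larynx and hypopharynx would then be grouped with salivary gland and sinus.
3. If the randomisation list can still be regenerated, stratify it by the same two factors. Two levels each gives four strata. If it cannot, the covariates alone recover most of the benefit.
4. Record both factors before randomisation. Section 5.1 describes chart review of treatment data after therapy, while the calendar puts the Appendix H form at baseline. The plan should say that the baseline values are used.
5. Mark the VHNSS at baseline in both calendars, so that the covariate already planned has data.

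The cost is two model terms, a few lines of text and possibly a new list. Site and setting need no new data collection. Item 5 adds one administration of a questionnaire that the appendix says takes under ten minutes, and the existing analysis already depends on it.

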4.0 Enrollment/Randomization

A total of 150 patients planned for primary and adjuvant radiation with or without chemotherapy will be recruited. These patients will be identified in the Vanderbilt Oncology Clinic and at head and neck tumor board. Study staff will approach patients to discuss the study and the possibility of patient participation therein. The objectives and requirements of the study will be described to the patients and any questions will be answered. Interested patients will be given consent for to review. If the patient volunteers to participate in the study, the consent will be signed and they will be given a copy for their records. The original copy will be retained in the study files. The patient will be assigned to the usual care or usual care plus gabapentin arm of the study according to the next group assignment specified in the randomization list generated via the use of a computer-generated, permuted block program developed by Co-I [name].

5.0 Study Procedures

5.1 Chemoradiation:

Chemotherapy and radiation will be instituted per standard of care. There will be no alterations in standard of care as a result of participation in this study. Disease treatment related data will be obtained through chart review after the completion of therapy.

5.2 Study Treatment:

Patients will be randomized to Arm 1 (Usual Care) or Arm 2 – (Usual Care plus Gabapentin).

Arm 1: Usual Care:

Usual care will include the following:

1. Oral health measures including brushing, flossing, and the use of fluoride toothpaste
2. Oral rinsing with baking soda and salt water gargles every 2-3 hours while awake
3. Miracle mouthwash formulated to include topical lidocaine, Benadryl, and Maalox;
4. Nonsteroidal anti-inflammatories around the clock to treat pain and inflammation
5. Opioid analgesics to include a fixed and breakthrough medication.

Patients will undergo an education session at the beginning of treatment to review foundations of oral care and pain management.

Arm 2: Usual Care plus Gabapentin.

Patients will receive all measures for Arm 1 **PLUS** Gabapentin. Gabapentin will be dose escalated using a slow escalation schema to minimize the sedating effects of medication and avoid undue toxicities:

- Week 1: Gabapentin 100 mg PO 3 times a day
- Week 2: Gabapentin 300 mg PO 3 times a day.
- Week 3: Gabapentin 600 mg PO 3 times a day.
- Week 4 onward: Gabapentin 900 mg PO 3 times a day.

The highest tolerated dose of gabapentin will continue throughout treatment. Missed doses, though regrettable, are part of any patient-administered medication and will not be considered deviations for this study as we are studying practical efficacy. After completion of therapy, mucositis is expected to resolve at a variable rate (1 to 3 months post treatment). Gabapentin will be continued until mucositis resolves **and** pain subsides. Patients will be weaned off opioids prior to initiation of gabapentin de-escalation. Once opioids have been weaned, de-escalation of gabapentin will be initiated. Since the rate at which patients can be weaned of pain medications is variable, de-escalation will be managed by the treating physician. Abrupt discontinuation of gabapentin will be discouraged in order to avoid symptoms related to withdrawal.

5.3 Dose Modifications:

Prior to each dose escalation, patients will be assessed for side effects related to gabapentin.

- Patients who are tolerating the current dosing schedule will undertake an escalation to the next dose level.
- If patients have mild to moderate side effects related to gabapentin, no further dose escalation will be undertaken
- If patients develop severe side effects attributable to gabapentin, gabapentin will be held until the side effects have totally resolved and then restarted at the last known tolerated dose level.
- Although rare, severe mood alterations and suicidal thoughts have been associated with this agent. Should patients experience these symptoms, gabapentin will be permanently discontinued.

5.4 Route of Administration:

Gabapentin is usually taken orally. Gabapentin may also be crushed and given via feeding tube if the patient is unable to swallow the tablet.

5.5 Pain Management:

Pain management for tumor and treatment related toxicities will be at the discretion of the treating physician. Opioid and adjuvant use will be documented for study purposes. At the completion of study, patients on Arm 1 may be started on gabapentin if they have uncontrolled mucositis associated pain. For patients assigned to Arm 1, the treating physician will manage the utilization of gabapentin during the post-treatment phase

5.6 Study Visits:

In order to minimize inconvenience to patients under study, study visits will coincide with scheduled treatment. This may introduce a degree of variability in the timing of weekly visits and follow-up visits which will be considered acceptable except in cases where explicit visit timing is dictated elsewhere in the protocol. Weekly on treatment visits that are more than 1 week late will be considered missing.

Baseline:

Prior to initiating therapy, patients will undergo education sessions with study staff. The educational intervention will include a discussion of oral health foundations as well as a discussion of pain management. This education is standardly applied to all VUMC patients undergoing radiation therapy for HNC and will not be otherwise documented. In addition, patients will also be given written material to review. Patient will be given a pain diary and instructed on its use. Baseline pain medication use will be documented. Patients will complete the demographic survey. Patients randomized to gabapentin will be given a prescription for gabapentin with dose escalation as noted in the treatment section. Patients who do not have insurance or who are unable to afford gabapentin will be provided with medication from the indigent pharmacy. All baseline assessments must be done within 4 weeks of starting concurrent chemoradiation.

Weekly On Treatment Visits:

Starting with the initiation of concurrent chemoradiation, patients will be evaluated on a weekly basis. The evaluation will include:

- 1) review of the weekly pain survey
- 2) for patients on gabapentin (Arm 2) --we will review their compliance log and identify any barriers to compliance and strategies to improve their compliance
- 3) adjustment of pain regimen
- 4) completion and review of the Vanderbilt head and neck symptom survey
- 5) mucositis grading.

End-of-Treatment Visit:

Patients will undergo an evaluation at their final radiotherapy visit or within 2 weeks after. This will include the following:

- 1) review of the monthly diary survey
- 2) for patients on gabapentin (Arm 2) --we will review their compliance log and identify any barriers to compliance and strategies to improve their compliance

- 3) adjustment of pain regimen
- 4) completion and review of the Vanderbilt head and neck symptom survey
- 5) mucositis grading.

6.0 Study Measures:

6.1 Mucositis Grading:

Patients will have an oral exam twice a week as part of standard of care. Mucositis will be graded based on the World Health Organization criteria. Mucositis assessments will be done by trained study staff.

6.2 Patient Reported Outcome Measures:

Study Visit: The study nurse will meet with the patient at baseline, weekly during radiation therapy, and at 1, 2 and 3 months post-treatment. At each study visit the study nurse will 1) administer appropriate questionnaires, 2) review the patient's pain diary and compliance diary, 3) document concurrent medications, 4) document toxicities based on CT CAE criteria 4.0, 5) identify and prepare reports for any adverse events, 6) document any dose adjustments in pain medications as recommended by the physician or nurse practitioner, and 7) educate the patient regarding medication dose and schedule.

As these patient reported outcome measures represent outcomes of interest for the study, they will not be altered by study staff due to missingness as changes would threaten the validity of the tool.

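### Low priority: the last solicited safety check is at month 3, but the gabapentin taper can run past it; tie Arm 2 adverse event collection to the last dose

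*Combined protocol and SAP*

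**What the plan says.** **When the drug stops.** Section 5.2 escalates the dose weekly to the top step ("Week 4 onward: Gabapentin 900 mg PO 3 times a day") or the highest dose tolerated. After treatment, "mucositis is expected to resolve at a variable rate (1 to 3 months post treatment). Gabapentin will be continued until mucositis resolves" and pain has also settled. "Patients will be weaned off opioids prior to initiation of gabapentin de-escalation", and "de-escalation will be managed by the treating physician". Neither a taper length nor a maximum duration is given. The section adds: "Abrupt discontinuation of gabapentin will be discouraged in order to avoid symptoms related to withdrawal".

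**When safety is asked about.** Under section 6.2 the study nurse sees the patient "at baseline, weekly during radiation therapy, and at 1, 2 and 3 months post-treatment". At each visit the nurse is to "document toxicities based on CT CAE criteria 4.0" and to record concurrent medication and changes in pain-medication dose. Both copies of the Appendix I calendar end with the month 1, 2 and 3 column, and section 10.0 also describes a follow-up of three months. Section 5.6 says of fitting study visits around treatment appointments: "This may introduce a degree of variability in the timing of weekly visits and follow-up visits".

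**Other relevant text.** Section 8.1 requires events of grade 3 or higher to be documented and sets no end date. The compliance diary in Appendix D ends when the patient answers that gabapentin is no longer taken, without asking for the date of the last dose. The closing paragraph of section 1.6 says that participation ends once therapy is complete.

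**The concern.** The stop of the drug depends on events in each patient, while the stop of solicited safety collection is fixed by the calendar. The plan's own upper figure for healing coincides with the last visit, and two further steps, the opioid wean and the taper, may still follow.

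Withdrawal symptoms would be expected during the taper and in the days after the last dose. For a late finisher those days have no scheduled study contact. The same holds for continued exposure: a patient with unresolved pain at month 3 may still be on up to 900 mg three times a day. Section 5.3 requires permanent discontinuation for severe mood change or suicidal thoughts, yet the last scheduled mood and neurotoxicity questionnaires are at month 3.

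Aim 3 counts grade 3 or 4 adverse events. At stake for these patients is whether an empty record means that nothing severe happened or that nobody asked.

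**Working it through.** The plan states no figure on this point, so there is none to reproduce. The check is a timeline.

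**Inputs from the documents**
- Healing at r = 1 to 3 months after treatment (section 5.2).
- Last solicited check at 3 months after treatment (section 6.2, Appendix I).
- Dose steps of 100, 300, 600 and 900 mg three times a day, one week per step on the way up (section 5.2).

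**Assumptions, because the documents are silent**
- Both intervals start at the end of treatment. This is the natural reading, but no section defines day 0.
- Pain has settled by the time the mucositis heals.
- Opioid wean after healing: w = 0 to 8 weeks. The wean may overlap with healing, in which case w is near 0.
- Taper length T: reversing the weekly steps takes 3 weeks from 900 mg (one week each at 600, 300 and 100 mg), 2 weeks from 600 mg and 1 week from 300 mg.

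**Step 1: time left at healing.** One month = 365.25 / 12 / 7 = 4.348 weeks, so month 3 = 13.0 weeks. Weeks left = (3 − r) × 4.348. This gives 8.7 for r = 1, 4.3 for r = 2, 2.2 for r = 2.5 and 0 for r = 3.

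**Step 2: latest healing time that still puts the last dose at or before month 3, with w = 0.** This is 3 − T / 4.348: month 2.77 for T = 1, 2.54 for T = 2 and 2.31 for T = 3. Any wean after healing moves these points earlier.

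**Step 3: taper after the last check.** Taper start = 4.348 × r + w. Taper end = start + T. Unchecked weeks = end minus the later of start and 13.0, or 0 if negative.

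| Healing (month) | Wean (weeks) | Taper (weeks) | Taper ends (week) | Unchecked taper (weeks) |
|---|---|---|---|---|
| 1 | 0 | 3 | 7.3 | 0 |
| 1 | 4 | 3 | 11.3 | 0 |
| 1 | 8 | 3 | 15.3 | 2.3 |
| 2 | 0 | 3 | 11.7 | 0 |
| 2 | 2 | 3 | 13.7 | 0.7 |
| 2 | 4 | 3 | 15.7 | 2.7 |
| 3 | 0 | 1 | 14.0 | 1.0 (all) |
| 3 | 0 | 3 | 16.0 | 3.0 (all) |

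Early healers with a short wean are covered throughout. For healing at month 3 the whole taper is unchecked even with no wean.

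**Step 4: sensitivity to day 0.** Suppose the month visits were counted from an end-of-treatment visit 2 weeks after chemoradiation, the timing given under the first Appendix I calendar. The last visit then falls at week 15.0. Healing at month 3 with no wean leaves 16.0 − 15.0 = 1.0 week of a 3-week taper unchecked and none of a 1-week taper. The gap shrinks but does not close.

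**The case against.** The strongest reply is that any fixed follow-up leaves a tail, and that this tail touches no stated outcome. The pain and opioid hypotheses are set at week 6. Aim 3 covers grade 3 or 4 events and stopping because of side effects, and section 10.0 summarises it by frequency distributions only. A planned taper is not a side-effect discontinuation, and milder withdrawal symptoms lie outside the aim. All of this stands, and it keeps the priority low.

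Second, a reader might infer that severe events after month 3 go unrecorded. The documents do not support that. The documentation rule in section 8.1 has no end date, participants are taught which events need urgent care, and a physician manages the taper. What remains is narrower: none of these provisions schedules a study contact, so capture depends on someone reporting unprompted.

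Third, the missing last-dose question in Appendix D is only a partial gap. Through month 3, the concurrent-medication and dose-change records in section 6.2 can show that a patient has stopped. They do not help after month 3.

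Fourth, the gabapentin row of Appendix I also ends at month 3, which could be read as the end of the drug. Section 5.2 sets no such stop, and a forced one could conflict with weaning opioids first.

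Finally, section 1.6 read literally would end observation at the end of therapy. A reader might conclude that no post-treatment safety data are planned. Section 6.2, both calendars and section 10.0 all provide for three months, so this is a sentence to align, not evidence of a larger gap.

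**Conclusion.** The point holds as a low-priority, inexpensive safety improvement. At the upper end of the healing range that the protocol itself expects, the taper falls after the last scheduled safety check, and no section closes the gap. The conclusion rests on two readings: that the month visits are counted from the end of treatment, and that section 5.2 sets no calendar stop for the drug.

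Its size in patients is unknown. It is tempting to assume a distribution of healing times and quote a share of Arm 2, but the documents give no such distribution, no opioid-wean length and no taper length, so any percentage would only restate the assumptions. The only bound available is the arm itself: 150 / 2 = 75 patients with equal allocation, or 120 / 2 = 60 after the planned 20% loss.

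Nor do the documents support reading this as a threat to the trial's comparisons. The week-6 outcomes and the by-arm safety summary through month 3 are unaffected.

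**What to change.** 1. State that adverse event collection in Arm 2 runs to month 3 or to a fixed short period after the last gabapentin dose, whichever is later. Thirty days is one reasonable choice; the documents do not dictate it.
2. For patients still on the drug at month 3, have existing staff make one brief check at the end of that period, by phone or chart review, and record the last-dose date.
3. List events after month 3 separately under Aim 3. Arm 1 has no matching extended collection, so these events should not enter the by-arm summary.
4. Reword the participation sentence in section 1.6 to agree with the above.

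De-escalation stays with the treating physician. Sample size, randomisation and the planned efficacy analyses do not change. The cost is a short wording change, one data field, one contact for each patient still on the drug at month 3, and slightly later database closure. For example, healing at month 3 with no further wean, a 3-week taper and a 30-day window gives 21 + 30 = 51 days beyond the month 3 visit.
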